**A randomized, controlled, double blind study to evaluate the efficacy
of intralesional triamcinolone in the treatment of hidradenitis
suppurativa**

STUDY PROTOCOL

NCT number NCT02781818
Document Date 11/30/2017

Last Update: 11/30/2017

Study Protocol

Title: A randomized, controlled, double blind study to evaluate the efficacy of intralesional triamcinolone in the treatment of hidradenitis suppurativa.

Purpose: To evaluate the effectiveness of intralesional triamcinolone for the treatment of hidradenitis suppurativa

Participants: Patients diagnosed with Hidradenitis Suppurativa that have active inflammatory HS lesions. Up to 60 lesions will be treated. Between 20 and 60 patients will be enrolled dependent on the number of lesions they have treated. (up to 3 per patient)

Procedures (methods): Injection of triamcinolone or placebo into active lesions of hidradenitis suppurativa.

Hidradenitis Suppurativa: Symptoms & Diagnosis

Three criteria must be present for the diagnosis of HS. Firstly, characteristic lesions must be present, often beginning as “blind boils” that transition to abscesses, bridged scars, draining sinus, and post-inflammatory “tombstone double-ended pseudocomedones.”¹ These lesions must be present in the typical areas: the groin, axillae, buttocks, perineal region, and infra- and intermammary folds.¹ The final criterion is that there must be a history of recurrence. The disease is typically chronic with relentless progression that frequently results in significant disability and quality of life impairment.

The acute, painful lesions have been reported to have an average duration of 6.9 days, but permanent painful boils are present in 62% of patients.² Patients develop a median of two lesions per month and average age of onset is 21.9 years.² Rupture of lesions can lead to worsening pain, suppurative discharge, and malodor.³ The current prevalence of HS has been reported to range from 0.05% to 4%, with the number of patients diagnosed substantially increasing in recent years.⁴ The rise in diagnoses is due to either increased knowledge of HS, increased ability to identify the clinical signs, or a true increase based on lifestyle modifications. ⁴

A dermatologist or healthcare professional with HS experience should make the diagnosis and determine the clinical stage. Hurley staging is a quick way to characterize staging of the condition and identify appropriate therapy and likely success of treatment. We will identify the Hurley staging for the involved sites during the study, as this may be helpful in characterizing our population.

Pathogenesis of Hidradenitis Suppurativa

The exact pathogenesis of HS remains unclear, but the hair follicle is most likely the location where the lesion originates. Recent investigations demonstrated that the interleukin-12/interleukin-23/Th17 pathway and tumor necrosis factor α are involved in HS, indicating that the pathogenesis is immune and inflammatory related.^{5, 6} Intralesional steroid injections are commonly used for localized inflammatory skin diseases, such as cutaneous lupus erythematosus, cystic acne, and sarcoidosis, so it seems appropriate that intralesional

triamcinolone will be beneficial for HS.⁷ HS may also be associated with comorbid diseases such as obesity, arthritis, anemia, lymphedema, and metabolic syndrome.⁸ These conditions should be addressed and appropriately managed by health care providers.

Treatment of Hidradenitis Suppurativa

HS is primarily treated with antibiotics, biologics, and surgery in severe cases. First line therapies are clindamycin lotion 1%, Tetracycline, Clindamycin/Rifampicin, and Adalimumab.⁹ Intralesional triamcinolone, the focus of our research study, is a common and routine treatment for acutely flaring HS lesions.

Hidradenitis Suppurativa Negatively Impacts Quality of Life

HS has a greater negative impact on quality of life than other more commonly known dermatologic conditions such as psoriasis, atopic dermatitis, acne vulgaris, and chronic urticaria.¹⁰ This is primarily due to the severe pain, discomfort, pruritus, and malodor associated with HS. Patients also often have an impaired sexual health, suffer from depression, and have a difficulty performing work responsibilities.¹¹ Out of employed HS patients, 58.1% report work absence due to the condition with a mean absence from work duration of 33.6 ± 26.1 days annually.¹⁰ Improving clinical outcomes, such as shortened outbreaks and diminished pain, could have a profound effect on patients' professional endeavors and quality of life.

Present Study

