**A randomized, controlled, double blind study to evaluate the efficacy  
of intralesional triamcinolone in the treatment of hidradenitis  
suppurativa**

STATISTICAL ANALYSIS PLAN

**NCT number** NCT02781818  
**Document Date** 05/17/2017

Date 5-17-2017

Statistical approach for IRB 16-0773, A randomized, controlled, double-blind study to evaluate the efficacy of intralesional triamcinolone in the treatment of hidradenitis suppurativa.

The calculations for power justification are outlined below demonstrating 80% power to demonstrate our primary aim. The power to tell a difference between our 2 treatment groups is only 28%, but this is acceptable as a secondary aim. In our final analysis we will use a mixed effects regression model to account for the variation in number of lesions evaluated in each patient. This will account for some correlation among lesions treated within the same patient due to how patient reported lesion clearance may be somewhat effected by individual patient perception. 95% confidence intervals will be created for each group and p-values for comparisons between each group will be calculated in the final analysis for each study end point.

Our secondary aim of finding differences in pain scores are appropriately powered with power nearing 100%.

For our third aim demonstrating improved perception of treatment, the analysis is more straightforward as data is gathered at only one time point. We will perform descriptive analysis and report the average ratings and the corresponding confidence intervals.

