#### **Simulation settings for power analysis**

There are 30 patients in which 12 have 1 lesion, 6 have 2 lesions and 12 have 3 lesions. Each lesion is then randomized to one of 3 treatment groups (say, A, B, C) with equal chance. For patient  $k$ , lesion  $j$ , let  $T$  be the treatment assigned. We generate data as following:

$$Y_{kj} = \beta_1 I(T_{kj} = A) + \beta_2 I(T_{kj} = B) + \beta_3 I(T_{kj} = C) + b_k + e_{kj}$$

$b_k$  is a patient-specific random effect,  $e_{kj}$  is a random error.

We consider two scenarios, where the first one corresponds to the outcome of days to resolution, and the second one is for the pain scores.

Scenario 1:

$$\beta_1 = 6, \beta_2 = 8, \beta_3 = 10;$$

$b_k$  is patient-specific random effect from normal with mean 0 and standard deviation  $5\sqrt{0.2}$ ;

$e_{kj}$  is random error from normal with mean 0 and standard deviation  $5\sqrt{0.8}$ .

Scenario 2:

$$\beta_1 = 2, \beta_2 = 4, \beta_3 = 6;$$

$b_k$  is patient-specific random effect from normal with mean 0 and standard deviation  $\sqrt{0.2}$ ;

$e_{kj}$  is random error from normal with mean 0 and standard deviation  $\sqrt{0.8}$ .

After simulating the data 100 times, we fit the same model, and perform two tests as follows:

- Test  $\frac{\beta_1 + \beta_2}{2} < \beta_3$ , report the probability of rejecting the null (one side p-value < 0.05), report the standard error of the estimates for  $\frac{\beta_1 + \beta_2}{2} - \beta_3$ .
- Test  $\beta_1 < \beta_2$ , report the probability of rejecting the null (one side p-value < 0.05), report the standard error of the estimates for  $\beta_1 - \beta_2$ .

The results are given in the following table. It shows that for the primary outcome (days to resolution), there is 80% power to test that the combined treatment groups have less number of the days than the control group. The power to detect the difference between two treatment groups is 28%. For the secondary outcome of the pain scores, these numbers become 100%.

The average 95% confidence interval for the difference between the combined treatment groups and the control group is (2.6, 5.6) for days to resolution and (2.46, 3.52) for pain scores.

Results of the two scenarios						
Scenario	Compare combined treatments vs control			Compare two treatment groups		
	$\frac{\beta_1 + \beta_2}{2} - \beta_3$	SE	power	$\beta_1 - \beta_2$	Std err (estimates)	power
	True value			True value		

1: days to resolution	-3	1.331	0.8	-2	1.540	0.28

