**Final analysis of data:**

For each aim we will calculate means with 95% confidence intervals and p-values for comparisons between each treatment group and the placebo group. The treatment groups will also be combined for comparison to the placebo group.

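### Hurley stage is to be recorded for the treated sites but has no prespecified place in the days-to-resolution model, which may give up some precision

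*Protocol*

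**What the plan says.** The protocol's background section on symptoms and diagnosis states: "Hurley staging is a quick way to characterize staging of the condition and identify appropriate therapy and likely success of treatment". It then commits to collecting the stage: "We will identify the Hurley staging for the involved sites during the study, as this may be helpful in characterizing our population". Describing the population is the only use it declares.

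The SAP's opening text gives one reason for its model: "In our final analysis we will use a mixed effects regression model to account for the variation in number of lesions evaluated in each patient". The only model written out is under Simulation settings for power analysis. It has three treatment terms, a patient random effect and an error term. Under Final analysis of data the SAP says: "For each aim we will calculate means with 95% confidence intervals and p-values for comparisons between each treatment group and the placebo group". It adds a comparison of the combined active groups with placebo.

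No baseline covariate is named anywhere in the SAP. That applies to Hurley stage and also to the lesion pain that the protocol's Study Design section records before injection. The Day 0 list in the Protocol summary includes history, medications and a physical exam, but does not mention Hurley staging.

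**The concern.** The protocol presents stage as informative about outcome and plans to collect it, yet the SAP gives it no analytic role. The trial is small, at up to 60 lesions or about 20 per arm, and no stratification is described. Eligibility is broad: nodules, abscesses, lesions over 2 cm and lesions associated with sinus tracts all qualify, so severity may vary a good deal. If stage predicts days to resolution, leaving it in the error term widens the confidence interval for the main contrast. The power calculation has little slack for that.

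There is also a prespecification issue. A SAP that is silent on covariates leaves the choice open until outcomes are known.

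**Working it through.** **Inputs from the SAP, Simulation settings for power analysis**

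- Sample: "There are 30 patients in which 12 have 1 lesion, 6 have 2 lesions and 12 have 3 lesions", so 12×1 + 6×2 + 12×3 = 60 lesions.
- Allocation: "Each lesion is then randomized to one of 3 treatment groups (say, A, B, C) with equal chance".
- Mean days 6, 8 and 10, so the main contrast is (6 + 8)/2 − 10 = −3.
- Total variance 25: between patients 25 × 0.2 = 5, between lesions 25 × 0.8 = 20.
- One-sided 0.05 test (z = 1.645); stated SE 1.331; stated power 80%; 100 simulation runs.

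**Assumptions not in the documents**

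- Share of variance explained by stage (R²): 0, 5, 10 or 20%.
- Stage mix 30/50/20%, with a linear effect across stages.

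**Step 1: the plan's own figure.** Re-simulating the SAP model with a REML random-intercept fit (3,000 runs) gives an SE of 1.330, which matches, and power of 72.7%, which does not. The stated SE gives the same answer: Φ(3/1.331 − 1.645) = Φ(0.609) = 72.9%. With 100 runs, 80 or more rejections at a true power of 72.7% has probability of about 6%, so simulation error can explain the stated 80%. The starting point here is therefore about 72–73%.

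**Step 2: closed form.** One added term gives SE_adj = 1.331 × √(1 − R²) × √(57/56), where 57 = 60 − 3 is the residual df before the term and 56 after it.

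- R² = 0: SE 1.343, a rise of under 1%.
- R² = 5%: SE 1.31, power 0.74.
- R² = 10%: SE 1.27, power 0.76.
- R² = 20%: SE 1.20, power 0.80.

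This formula suits only a stage that varies freely between lesions. If a patient's lesions share a stage, the patient random effect already absorbs part of it.

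**Step 3: both cases under the SAP's patient structure.** Generalised least squares at the SAP's variances, random allocation, one ordinal stage term, 6,000 runs per setting. Unadjusted: mean SE about 1.356, one-sided power 71.5%. This starts slightly lower than Step 1 because arm sizes vary by chance; with exactly 20 lesions per arm it is 1.332 and 72.8%.

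| Variance explained | Power, stage varies by site | Power, stage constant within patient |
|---|---|---|
| 0% | 70.8% (−0.7) | 71.0% (−0.5) |
| 5% | 72.9% (+1.4) | 72.3% (+0.8) |
| 10% | 75.1% (+3.6) | 73.6% (+2.1) |
| 20% | 79.9% (+8.4), SE 1.208 | 77.2% (+5.7), SE 1.256 |

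Brackets show the change in points from 71.5%. In the right-hand column, 20% is a ceiling, because it is all of the between-patient variance (5 of 25). Break-even is at about 2–3% of variance explained. Entering stage as two indicator terms instead moves break-even to roughly 3–5%, and power at 0% explained is then 70.2–70.6%.

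**Step 4: pain.** The SAP's table gives power of 1 for both pain comparisons. On the plan's own figures there is no power to gain for day-5 pain.

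**The case against.** The strongest reply is that nothing here is an error. The protocol says stage is collected to describe the population, and the SAP is consistent with that. Randomisation protects the comparison, and the unadjusted SE already allows for chance imbalance. Both statements are correct.

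The reply can go further. The sentence linking stage to treatment success is general background on the disease. It does not address patient-reported resolution of one injected lesion over 14 days, and no effect size is given. A marker of treatment success might also modify the treatment effect, which a main-effect term would not capture. This stands as well. It is why the gain is shown as a range that starts below zero.

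The patient random effect does take up part of a stage shared by a patient's lesions, but only part: some gain remains in the constant-within-patient column from 5% explained upward.

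Two facts are less firm than they look. Equal-chance allocation by lesion is described in the power simulation; the protocol says only that each lesion is randomised. Staging before injection is an inference from Day 0 being the only visit described, since the protocol's own words are that staging happens during the study.

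None of this removes the modest point that the SAP should say whether stage enters the model.

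**Conclusion.** The point holds as an optional improvement. A variable the protocol considers informative is to be collected but has no stated analytic role, and the days-to-resolution contrast may lose some precision as a result. For 5–20% of variance explained, the gain in one-sided power is about 1 to 8 points if stage varies by site and about 1 to 6 if it is constant within a patient. If stage explains nothing, the loss is under 1 point. These figures rest on the assumed variance shares and stage mix, a linear stage effect, and the SAP's normal model with its stated variances.

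A reader might infer four stronger things that the documents do not support:

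- That precision is definitely lost. No variance share is given, and below about 2–3% there is no gain.
- That the SAP excludes stage. It leaves covariates unspecified; the bare model belongs to the power simulation.
- That the unadjusted comparison is biased. Lesions are randomised.
- That adjustment would restore the stated 80% power. It comes close only with 20% explained and stage varying by site. The gap between 80% and about 73% is a separate matter.

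**What to change.** In the protocol's Day 0 procedures, state that the Hurley stage of each treated site is recorded before injection.

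In the SAP, before unblinding, add a sentence to this effect: the mixed model for days to resolution includes Hurley stage of the treated site as one ordinal fixed effect (1 df); the adjusted contrast of combined triamcinolone versus saline is the main estimate; the unadjusted contrast is reported as a sensitivity analysis. The same sentence should say whether any other baseline covariate, such as recorded lesion pain, enters the model. The change is not proposed for day-5 pain.

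The cost is one SAP sentence, one model term and one explicit entry on the Day 0 record for a value the protocol already plans to collect. There are no extra visits and treatment does not change. The statistical price, if stage proves uninformative, is an SE about 1% larger, so this is cheap rather than free.

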chronic HS lesion defined by tunneled lesion with multiple openings to the surface of the skin. Sinus tracts without associated nodules or abscesses will not be treatment targets.

4. Patient must be off of antibiotics or on a stable course of oral antibiotics for >4 weeks prior to the baseline visit. Allowable antibiotics during treatment course are topical clindamycin, topical chlorhexidine gluconate, oral doxycycline, oral minocycline, or oral clindamycin +/- rifampin.
5. Must be able to provide adequate informed consent for themselves

Exclusion Criteria:

1. Any patient with signs of active infection at the time of screening that is not related to their hidradenitis suppurativa.
2. Patients who have been on non-permitted antibiotics in the 4 weeks prior to baseline. Allowable antibiotics during treatment course are topical clindamycin, topical chlorhexidine gluconate, oral doxycycline, oral minocycline, or oral clindamycin +/- rifampin.
3. Patients who have had surgical intervention of the treated body region (i.e., right axilla) beyond incision and drainage procedures in the last 8 weeks or with open surgical wounds in the treatment region.
4. Patients who have been started on immunomodulatory or biologic treatment (i.e., adalimumab, infliximab) in the past 4 weeks
5. Patients on non-stable doses of opiate analgesics for the last 14 days prior to screening
6. Patients with history of hypersensitivity reactions to triamcinolone
7. Ongoing health or physical exam concerns which the investigator feels may put the patient at significant risk

Study Design

This will be a randomized, double-blind, placebo-controlled trial of two concentrations of intralesional triamcinolone, triamcinolone 40mg/ml and triamcinolone 10mg/ml, with normal saline as a placebo control. Target enrollment is up to 60 lesions with 1-3 lesions treated in each patient enrolled. Screening will be performed during regularly scheduled clinic visits with the principal investigator ([name]). Informed consent will be signed by the subject. Physical exam will be performed to assure that inflammatory lesions suitable for treatment are present. Once subjects are deemed appropriate for the study, between one and three treatment sites will be marked with sequential lettering with a skin marker and documented by body location. Pain level of each lesion will be recorded. At that time the triamcinolone and/or placebo will be prepared by the co-investigator the drug will be concealed with opaque tape on the syringe. The principal investigator and subject will thus be blinded as the principal investigator administers the treatment.

Following treatment, subjects will be given a paper questionnaire that will ask them to rate their level of pain on a 1-10 scale, the effectiveness of the treatment, and whether they believe the target lesions has resolved. They will record these scores on days 1, 2, 3, 5, 7, 10, and 14. These will be patient-reported outcomes only without any physician assessment as this is felt to be a more clinically relevant outcome. The principal investigator or co-investigator will contact subjects by phone to ensure that logs recording pain and days to resolution are completed in a timely and correct manner, but no data will be collected during the 14-day period in which questionnaires are completed to avoid influencing subject responses at the time of contact. After the final questionnaire is completed (more than 14 days after the intervention is performed), the

co-investigator or principal investigator will contact the subject by phone to remind the subject to mail in their questionnaires and may allow the option to collect the data that the subject has already recorded. At this time, the principal or co-investigator may also ascertain if any previously unreported adverse events occurred during the study period. The days to resolution reported and pain data will be used to compare the effects of varying concentrations of intralesional triamcinolone with normal saline.

Protocol summary:

Day 0: Subject recruited and pre-screened,

- Adult subjects will sign adult consent form and HIPAA authorization
- Subjects aged 16-17 will sign the age 15-17 assent form and parents will sign the parental consent form. HIPAA authorization will be signed.
- History of disease and medications will be taken
- Physical exam will be performed to see if appropriate target lesions are present
- Each lesion will be randomized to a treatment group
- Treatment will be administered via intralesional injection by the principal investigator
- Follow-up paper and pencil questionnaire will be dispensed along with a stamped and addressed return envelope.

Day 1, 2, 3, 5, 7, and 10:

- subject will complete corresponding section of the paper and pencil questionnaire on each of these days to report pain level of each lesion treated and whether each lesion has resolved.
- between day 2-7 the subject will be contacted by phone and reminded to complete their questionnaires. No data will be gathered at this time.

Day 14: subject will complete corresponding section of the paper and pencil questionnaire on each of these days to report pain level of each lesion treated and whether each lesion has resolved. He/she will also answer a question regarding how they view the efficacy of the treatment for each location

Day 14-21:

- investigator or co-investigator will contact the subject by phone to remind the subject to mail the completed questionnaire or allow the option collect the data on pain, lesion resolution, and efficacy that was previously recorded during the study period over the phone. At that time, the primary or co-investigator may ascertain if any adverse effects have occurred that have not already been reported.

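### The 80% power for days to resolution is not reached even at the protocol's maximum of 60 complete lesions (about 72–73%), and nothing allows for fewer lesions or lost diaries

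*Protocol*

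**What the plan says.** The protocol gives the lesion count twice, each time as an upper limit: "Up to 60 lesions will be treated" in the opening Participants paragraph and "Target enrollment is up to 60 lesions with 1-3 lesions treated in each patient enrolled" under Study Design. The only lower bound is on patients: "Between 20 and 60 patients will be enrolled dependent on the number of lesions they have treated". Neither document states a minimum number of lesions, a rule for ending enrolment, an attrition allowance or a rule for a missing diary.

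The SAP's section on simulation settings fixes the design it evaluates: "There are 30 patients in which 12 have 1 lesion, 6 have 2 lesions and 12 have 3 lesions". Allocation is by lesion: "Each lesion is then randomized to one of 3 treatment groups (say, A, B, C) with equal chance". Every simulated lesion has an outcome. The number of replicates is small: "After simulating the data 100 times, we fit the same model, and perform two tests as follows". The results table reports a standard error of 1.331 and power of 0.8 for combined treatments versus control on days to resolution. The SAP's opening section repeats the 80% as the power for the primary aim.

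All outcomes come from a paper questionnaire that the patient mails back. Under the protocol's Study Design and Protocol summary, entries already recorded may instead be taken by phone after day 14.

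**The concern.** The simulated 60 lesions are the most the protocol allows, and the count is of lesions treated, not lesions with data. Recruiting fewer, or losing diaries, can therefore only lower power, and replacing lost lesions beyond 60 is not provided for. Since one patient contributes up to three lesions, one lost diary can remove three outcomes. It also has to be asked whether the 80% is right at 60 lesions in the first place.

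At stake is how the primary result is read. A null finding would be judged against 80% power that the trial may never have had. A reader who sees a final count below 60 could not tell from the documents whether that was planned.

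**Working it through.** **Inputs** (SAP, simulation settings, Scenario 1). Mean days 6, 8 and 10, so combined active minus control is (6 + 8)/2 − 10 = −3. Patient SD 5√0.2 and residual SD 5√0.8, so total SD is 5 and intraclass correlation 0.2. Test one-sided at 0.05. Lesions: 12×1 + 6×2 + 12×3 = 60. Stated SE 1.331; stated power 0.80.

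**1. The plan's own figure.** Power = Φ(3/SE − z).
- One-sided: 3/1.331 = 2.254; 2.254 − 1.645 = 0.609; Φ(0.609) = 0.729.
- Two-sided: 2.254 − 1.960 = 0.294; Φ(0.294) = 0.616. This is shown because the SAP's final analysis promises 95% intervals and p-values without stating sidedness.

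The stated SE and the stated power do not match: 73%, not 80%.

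**2. Check on the SE.** Generalised least squares on the SAP's model, with variance components 25×0.2 = 5 and 25×0.8 = 20, averaged over 4,000 random allocations of the 60 lesions, gives a mean SE of 1.36 and mean power of 71.5% one-sided (60% two-sided). Refitting the mixed model to 1,000 simulated trials gives SE 1.38 and power 72.3%. The SE is approximately reproduced; the 80% is not. Other ways of making 60 lesions within the protocol do no better: 20 patients × 3 gives 72.3%, 30 × 2 gives 71.2%, 60 × 1 gives 69.6%.

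**3. Could the gap be simulation noise?** With 100 replicates, the Monte Carlo SE of an 80% estimate is √(0.8×0.2/100) = 4 points. If true power is 73%, the chance of 80 or more rejections in 100 is 0.07. The comparison of the two active groups misses in the other direction: Φ(2/1.540 − 1.645) = 36% against the stated 28%, and the chance of 28 or fewer rejections is 0.05. Misses in opposite directions point to noise more than to a consistent error.

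**4. Fewer evaluable lesions.** SE(n) = 1.331 × √(60/n).

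| Evaluable lesions | SE | One-sided | Two-sided |
|---|---|---|---|
| 60 | 1.331 | 73% | 62% |
| 54 | 1.403 | 69% | 57% |
| 48 | 1.488 | 64% | 52% |
| 40 | 1.630 | 58% | 45% |

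**5. Whole-patient diary loss.** Starting from 60 lesions in the SAP's mix and dropping patients at random (rates assumed), the least-squares calculation gives one-sided power of 70% at 5% loss, 67% at 10%, 65% at 15% and 63% at 20%.

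**6. Lesions needed for 80%.** The SE must be 3/(1.645 + 0.842) = 1.206, so n = 60 × (1.331/1.206)², about 73 evaluable lesions. The least-squares calculation gives about 76. Both exceed the maximum.

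**7. Pain scores.** Under Scenario 2, least squares keeps combined-versus-control power near 100% even at 20 lesions, and the comparison of the two active groups at about 96%.

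**The case against.** The strongest reply is that the documents agree on 60. Study Design calls it the target, the SAP simulates it, and the 20-to-60 patient range is what a 60-lesion target yields: 20 × 3 = 60 and 60 × 1 = 60. A reader might infer that the trial may stop anywhere below 60. That goes too far, because the Participants paragraph does set a floor of 20 patients. What stands is that 60 is never stated as required. Read literally, the floor permits 20 lesions, where one-sided power would be about 33%.

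The retention measures also deserve credit: a stamped return envelope, a reminder call between days 2 and 7, and a call between days 14 and 21. A partly filled diary can already show resolution. These steps may keep losses low, but the phone option recovers only what was recorded, and none of them is an allowance in the sample size.

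A reader might take the 80% as correct at 60 lesions and blame any shortfall on the ceiling. The drop from 80% to 73% has nothing to do with the ceiling; it lies in the power figure itself. Only the further fall below 73% comes from fewer lesions.

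A reader might also infer that an open-ended stop inflates the false-positive rate, since the co-investigator who prepares the syringes may later collect scores. The documents do not support this. They describe no interim look, the SAP speaks only of a final analysis, and nothing says that the co-investigator decides when enrolment ends. Any inflation figure would rest on an invented schedule of looks. Who handles both syringes and scores is a separate blinding question.

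**Conclusion.** The point holds for days to resolution. One-sided power at 60 complete lesions is about 72–73% (60–62% two-sided), so the stated 80% is not delivered even at the most favourable count the protocol allows. It falls to 69%, 64% and 58% at 54, 48 and 40 evaluable lesions, or to about 67–63% if 10–20% of patients return nothing.

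The figure at 60 lesions rests only on the SAP's own effect, SD and correlation. Attributing the 80% to chance is an inference, since the simulation output is not shown. The loss rates are assumptions, and 54, 48 and 40 are illustrative counts. The point does not extend to the combined-versus-control pain comparison, and it makes no claim about type I error.

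**What to change.** **SAP, opening section and simulation settings.** Replace the 80% with power recomputed from many more replicates. For example, 10,000 would give a Monte Carlo SE of √(0.72×0.28/10,000), about 0.4 points. Show one row each for 60, 54 and 48 evaluable lesions, and recompute the 28% in the same run.

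**Protocol, Participants paragraph and Study Design.** Replace the upper-limit wording with 60 lesions treated, and state that enrolment ends at that number without reference to outcome data by arm.

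**Cost.** A rerun of the simulation and wording in both documents. The stated power becomes less favourable, and the sponsor gives up the freedom to stop below 60.

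These changes describe the design correctly but do not restore 80%. If the sponsor wants that power, the maximum itself must rise. Keeping 60 evaluable lesions would take 60/0.9 = 67 treated at 10% loss or 60/0.8 = 75 at 20%, and 80% power would need about 73–76 evaluable. That is added recruitment, not a wording change.
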